## **19. Proposition and validation of a predictive tool for pre-hospital rule-out and rule-in**

The cohort will be divided into two parts: two thirds for learning and one third for validation. The description of the two samples will be performed with the same baseline variables listed in the section 16. No p-value will be computed because of the random allocation of the patients. Instead, standardized mean differences will be estimated to evaluate the comparability of the two samples.

From the learning sample, a logistic model will be estimated with LASSO penalization to select the subset of predictors among the following list of candidates: age, gender, body mass index, active smoking, stented heart disease, bypassed heart disease, compatible clinical history, delay after onset of pain lower than 3h; normal ECG evaluated by the HEMS, and the following risk factors: hypertension, diabetes, hypercholesterolemia, family history and hs-cTnI. The outcome will be the diagnosis of NSTEMI. We will perform a 20-fold deviance-based cross-validation to choose the best tuning parameter.

A particular attention will be paid to the interaction between hs-cTnI and the delay after onset of chest pain because the level of troponin may continue to grow up to three hours after the chest pain. This may lead to increase the proportion of false negatives.

From the validation sample, we will estimate its discriminative capacities by the ROC curve and the related AUC. Its goodness-of-fit will be evaluated by a calibration plot of the observed probabilities against the mean predicted probabilities for five subgroups of equal size. The corresponding Hosmer and Lemeshow statistic will be estimated.

Always from the validation sample, we will compute the in-hospital HEART score at 0h, the related ROC curve and AUC, and its difference with the pre-hospital predictive model.

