## **10. Sample size**

For the primary objective, we expect a sensitivity of 95%. We aim to include 73 patients for a maximum length of the 95% confidence interval equals 10% (+/-5%). Assuming a NSTEMI prevalence of 10%, 730 patients must be analyzed to achieve this precision. By anticipating a 10% rate of non-exploitable data (missing value, lost to follow-up, etc.), 800 inclusions are necessary.

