## **20. Investigation of the utility of the prediction model**

From the validation sample, we will estimate its ability to rule-out the patients instead of the hospitalization. For that purpose, we will estimate the percentage of event-free patients at hospital discharge (no NSTEMI) among the ones with a predicted probability of event less than 0.3. We will also estimate the percentage of patients with a predicted probability of event less than 0.3.

From the validation sample, we will estimate its ability to rule-in the patients instead of the in-hospital evaluation at 0h by the percentage of patient with the event (NSTEMI) among the ones with a predicted probability of event higher than 0.65. We will also estimate the percentage of patients with a predicted probability of event higher than 0.65.

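### At the planned 10% prevalence, the five-group calibration check draws one point for the whole range containing both decision cut-offs, so it cannot show calibration around 0.3 or 0.65

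*SAP*

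**What the plan says.** SAP section 19 divides the cohort into "two thirds for learning and one third for validation". In the validation part, goodness-of-fit is judged by "a calibration plot of the observed probabilities against the mean predicted probabilities for five subgroups of equal size". It adds: "The corresponding Hosmer and Lemeshow statistic will be estimated". No calibration intercept, slope or smooth curve is planned, and the degrees of freedom for the statistic are not given.

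Section 20 works with absolute predicted risks. For rule-out it reports the share of patients predicted below 0.3 and the percentage of them without NSTEMI. For rule-in it reports the share predicted above 0.65 and the percentage with NSTEMI "among the ones with a predicted probability of event higher than 0.65". Section 7 gives the targets: an NPV of 99% in at least 5% of patients and a PPV of 65% in at least 10%.

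Section 22 makes the use of B-splines depend on a poor goodness-of-fit. The planning figures are in section 10: "Assuming a NSTEMI prevalence of 10%, 730 patients must be analyzed to achieve this precision".

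**The concern.** A tool applied at fixed absolute risks needs to be calibrated near those risks. Equal-size groups place their points where the patients are. With a 10% event rate, most patients have low predicted risks, so most of the points describe risks well below 0.3. All patients around and between the two cut-offs are averaged into one point.

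If high predictions are too extreme, as can happen with a model developed on few events, that average can look acceptable while patients above 0.65 do clearly worse than predicted. The same check also decides whether the spline remedy in section 22 is used, so a check that is weak in this range weakens that trigger too.

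**Working it through.** **The plan's own figures.** Section 10 expects a sensitivity of 95% within ±5 points: n = 1.96² × 0.95 × 0.05 / 0.05² = 72.99, so 73 NSTEMI patients, and 73 / 0.10 = 730 analysed. Allowing for 10% unusable data gives 730 × 1.1 = 803 or 730 / 0.9 = 812, against the stated 800. Nothing below depends on that difference.

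**Validation sample.** 730 / 3 ≈ 243 patients; 243 × 0.10 ≈ 24 events; 243 / 5 ≈ 49 patients per group.

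**Where 0.65 falls.** If predictions average 0.10, the share at or above a value c cannot exceed 0.10 / c. For 0.65 this is 0.10 / 0.65 = 15.4%. That is below 20%, so 0.65 must lie in the top fifth.

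**Where 0.3 falls.** The same bound is 0.10 / 0.3 = 33%, which does not settle it. A model is needed. The check used a calibrated two-normal model: d = √2 × Φ⁻¹(AUC), with logit risk = ln(0.10/0.90) + d·x − d²/2. The SAP gives no AUC, so a range is assumed.

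| AUC (assumed) | Top fifth starts at | Mean prediction in top fifth | Share > 0.3 | Share > 0.65 | Patients > 0.65, of 243 |
|---|---|---|---|---|---|
| 0.80 | 0.153 | 0.29 | 6.7% | 0.5% | 1.3 |
| 0.85 | 0.149 | 0.33 | 8.7% | 1.5% | 3.7 |
| 0.90 | 0.134 | 0.38 | 10.1% | 3.2% | 7.8 |
| 0.95 | 0.098 | 0.44 | 10.9% | 5.6% | 13.6 |

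In 20,000 simulated samples of 243 at each AUC from 0.75 to 0.95, both cut-offs lay in the top fifth every time.

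**Dependence on prevalence.** At 15%, at most 16.9% of patients exceed 0.3, so both cut-offs stay in the top fifth. At 20% with an AUC of 0.75 or more, 21% to 24% exceed 0.3, so 0.3 moves into the fourth fifth.

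**What one point can hide.** Take AUC 0.90 and predictions too extreme by a factor of 1.5 on the logit scale, with the mean kept at 10% (an illustration; the SAP gives no such figure).
- Top fifth: predicted 0.44, observed 0.38, a gap of 0.06. With 49 patients the standard error of the observed rate is √(0.38 × 0.62 / 49) = 0.07, so the gap is within one standard error.
- Predictions from 0.2 to 0.4: 0.29 against 0.26, a gap of 0.03.
- Predictions above 0.65: 0.85 against 0.71, a gap of 0.14. These are 5.4% of patients, about 13 of 243.

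The plotted point mixes these gaps. The lower groups also move (fourth fifth: 0.047 predicted, 0.078 observed), so the Hosmer-Lemeshow statistic retains some sensitivity.

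**Detecting over-extreme predictions (AUC 0.85, n = 243).** Simulations with somewhat different results agree in direction. At a true calibration slope of 0.7, Hosmer-Lemeshow detects the problem in 41% to 49% of samples and a slope test in 54% to 55%. At slope 0.6 the figures are 68% to 71% and 82% to 85%.

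**Bands set by the plan's cut-offs.** Below 0.3, from 0.3 to 0.65, and above 0.65, the 243 patients split about 222 / 17 / 4 at AUC 0.85 and 218 / 17 / 8 at AUC 0.90.

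**The case against.** The strongest reply is section 20 itself. The tool is used as two regions, and the SAP reports the observed event rate above 0.65 and the event-free rate below 0.3, with targets in section 7. In the illustration, the 0.71 would be printed. A reader might infer from the grouping that miscalibration where the tool is used would go entirely unseen. The SAP does not support that: gross failure of the rule-in group would show. This part of the reply stands. It is incomplete, because no comparison with the mean predicted risk is planned, the 0.3 to 0.65 range is not described, and the figure below 0.3 averages about 89% to 93% of patients (AUC 0.80 to 0.95), so it says little about risk near 0.3.

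The four lower points do cover most of the rule-out region. That also stands; the gap is the neighbourhood of the cut-offs.

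A reader might also conclude that the Hosmer-Lemeshow test is invalid because 3.2 to 4.0 of the 5 groups have fewer than 5 expected events on average. The simulations do not bear this out. With 5 degrees of freedom, false rejection is 5% to 7%, close to nominal. The inflated 12% to 17% arises only with 3 degrees of freedom, a choice the SAP does not make.

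Finally, a smooth curve cannot create information. A three-knot spline curve at 0.65 has a median 95% interval of about 0.38 to 0.85 at AUC 0.85 and 0.43 to 0.82 at AUC 0.95. LASSO shrinkage also works against over-extreme predictions. Both points stand. They are reasons to add to the planned check rather than replace it, and to show the intervals.

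**Conclusion.** The point holds in a limited form. At 10% prevalence the planned plot and Hosmer-Lemeshow statistic merge all predictions above about 0.10 to 0.15 into one group of about 49 patients, so they cannot resolve calibration around 0.3 and 0.65. For 0.65 this follows by arithmetic if predictions average about 10%. For 0.3 it rests on the two-normal model with AUC 0.75 to 0.95, and it no longer holds at about 20% prevalence with an AUC of 0.75 or more. It is therefore a consequence of five groups combined with a low event rate, and not of five groups as such.

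The gain from the better summary is modest: about 5 to 14 percentage points more detection at slope 0.7, and 11 to 17 at slope 0.6, taking the extremes of the ranges above. The method in section 19 is conventional and contradicts nothing else in the SAP. This is a minor-to-moderate improvement to a secondary objective, worth making because it costs almost nothing. The primary analysis is unaffected.

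**What to change.** In section 19, keep the five grouped points as an overlay. Add the calibration intercept and slope with 95% CIs, and a smooth calibration curve (loess or spline) with a confidence band.

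In section 20, report the mean predicted risk beside each observed percentage, with a 95% CI. Do this below 0.3, above 0.65, and for the 0.3 to 0.65 band, which is not described at present.

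In section 22, judge goodness-of-fit from the intercept and slope rather than from Hosmer-Lemeshow alone. If that statistic is kept with a p-value, state its degrees of freedom.

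The cost is some SAP wording and standard code, with slightly more analysis and no new data. Estimates near 0.65 will be imprecise because few patients have predictions that high, and the intervals should make this plain.

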## 5. Background and rationale of study

Chest pain (CP) is a difficult symptom to apprehend in the out-of-hospital setting, due to the complexity required to reliably assess patients over the phone. The current standard of care implies dispatching an out-of-hospital vector (HEMS) in the case of CP highly evocative of acute myocardial infarction (AMI). Risk stratification then requires the collection of a detailed medical history, a physical exam, before performing a 12 and 18-lead ECG.

In the absence of ST-segment deviation, single or trending cardiac troponin levels guide decision making. Few prospective trials evaluate the impact of point-of-care (POC) troponin on prehospital triage of CP and two prospective studies evaluating POC troponin as a clinical decision guide are currently underway.

High sensitivity assays improve patient outcomes by providing a better negative predictive value (NPV) and better rule-in for type 1 and 2 MI. High sensitivity cardiac troponin T (hs-cTnT) and I (hs-cTnI) are now routinely available on POC devices. The Atellica VTLI device offers the possibility of analyzing venous whole blood or capillary samples and returning hs-cTnI values comparable to central laboratory testing. The added advantage of hs-cTnI as opposed to hs-cTnT or standard troponin (cTnT) is its better NPV in ruling out coronary causes of CP. This biomarker offers the added advantage of being highly specific to myocardial injury and is correlated to the degree of muscle necrosis.

The hypothesis of the study is that the use of the high-sensitivity troponin I (hs-cTnI) could be of interest to stratify chest pain patients in pre-hospital setting.

[figure not shown]

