## 7. Objectives and related endpoints (units and calculations used to derive outcomes)

An adjudication committee oversees the validation of the events considered in the following objectives and outcomes.

The primary objective is to determine the thresholds of the pre-hospital capillary and venous hs-cTnI that maximizes the Youden J index. The event to predict is the non ST-elevation acute coronary syndrome at hospital discharge (NSTEMI). The sensitivity is the proportion of patients with an hs-cTnI level higher or equal to the threshold among the patients with the syndrome. The specificity is the proportion of patients with an hs-cTnI level lower than the threshold among the patients without the syndrome. We will also determine the ROC (receiver operating characteristic) curves and the related areas under the curve (AUC) related to the two methods.

**Figure 1.** Decision tree for ruling-out ruling-in the patients with a suspicious myocardial infarction after their emergency admission.

The secondary objectives of the VALIDATE project are to study the discriminative capacities of the pre-hospital hs-cTnI measured by two different testing methods (capillary and venous whole blood), and to select the method with the best performances. For that purpose, we aim:

- To evaluate the most relevant hs-cTnI measurement between the capillary- and the venous-based methods by i) reporting the concordance between the pre-hospital hs-cTnI measured by the capillary and venous methods, and ii) comparing the related AUCs for discriminating patients with NSTEMI.
- To estimate and compare the discriminative performances of the two methods by considering the Major Adverse Cardiac Events (MACE) occurrence at 30 days (ROC curves, AUCs, and Youden J index). Note that a NSTEMI systematically implies an outcome of MACE at 30 days.

Depending on the results at this stage, the rest of the analyses will be performed according to the venous or the capillary method, depending on their discriminative performances. In case of an equivalence, we will choose the capillary method because of its feasibility in a real-life setting. We will further investigate its usefulness to improve the ruling-in and ruling-out process described in Figure 1. More precisely, we aim:

- To propose a pre-hospital predictive tool of the probability of NSTEMI at hospital discharge. The candidate predictors will be the available demographic, clinical data, and pre-hospital hs-cTnI level.

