- To estimate its discriminative capacities by estimating the AUC and comparing its value with the one of the in-hospital HEART score estimated at 0h.
- To estimate its ability to rule-out the patients instead of the in-hospital evaluation at 0h for relieving emergency services, i.e., to achieve a negative predictive value equals to 99% (3) for at least 5% of the patients.
- To estimate its ability to rule-in the patients in the cardiology department instead of the in-hospital evaluation at 0h for reducing the time to treatment of the MI, i.e., to achieve a positive predictive value equals to 65.0% (Figure 1) for at least 10% of the patients.
- To evaluate its increase of capacities for discriminating patients with NSTEMI by considering additionally the venous troponin measured in hospital (difference in the AUC).

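### No model without pre-hospital hs-cTnI is planned, so the SAP cannot estimate how much of the tool's performance is due to that test

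*SAP*

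**What the plan says.** Section 5 states the hypothesis that "the use of the high-sensitivity troponin I (hs-cTnI) could be of interest to stratify chest pain patients in pre-hospital setting". The primary objective (Sections 7 and 18) examines hs-cTnI alone, by Youden threshold, ROC curve and AUC.

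Section 7 then has one sampling method chosen, capillary or venous, and continues: "We will further investigate its usefulness to improve the ruling-in and ruling-out process described in Figure 1". The vehicle for this is a pre-hospital prediction tool: "The candidate predictors will be the available demographic, clinical data, and pre-hospital hs-cTnI level".

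In Section 19, "a logistic model will be estimated with LASSO penalization to select the subset of predictors among the following list of candidates". The list has 14 entries: 13 demographic, clinical, ECG and timing variables, and hs-cTnI. Section 19 also gives attention to the interaction of hs-cTnI with the delay since pain onset.

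Two AUC comparisons are planned for the tool:
- With HEART at 0h (Sections 7 and 19): "we will compute the in-hospital HEART score at 0h, the related ROC curve and AUC, and its difference with the pre-hospital predictive model".
- With the tool extended by the in-hospital sample (Section 7): "To evaluate its increase of capacities for discriminating patients with NSTEMI by considering additionally the venous troponin measured in hospital". Sections 19 and 20 do not take this objective up.

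Section 20 reports the share of patients below a predicted probability of 0.3 and above 0.65, and the outcome in each group, for the full tool only.

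**The concern.** The HEMS team already has history, ECG, age and risk factors without a point-of-care device. The practical question about the device is what hs-cTnI adds to them, and the plan contains no analysis of those data on their own. It does plan an increment analysis for the in-hospital troponin, but none for the pre-hospital one, which is the index test.

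Without that reference, a good result against HEART might come from better-weighted clinical variables that need no device. A poor result might hide a real gain from the test. The same applies to the rule-out and rule-in shares in Section 20.

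**Working it through.** **1. What each planned analysis can show about the gain from pre-hospital hs-cTnI**

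| Planned analysis | Section | Does it isolate the gain? |
|---|---|---|
| hs-cTnI alone: threshold, AUC | 7, 18 | No. A marker can discriminate alone and add little to ECG and history |
| Selection by LASSO | 19 | No. Retention shows selection, not the size of the gain |
| Tool versus HEART at 0h | 7, 19 | No. The two differ in setting, timing and scoring as well |
| Tool plus in-hospital troponin | 7 | No. It measures the gain from the later sample |
| Shares below 0.3 and above 0.65 | 20 | No. Full tool only |

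**2. Illustration for the AUC.** The SAP gives no AUCs, so these are assumptions: tool 0.85, HEART 0.80.
- Planned result: 0.85 − 0.80 = 0.05.
- If the clinical-only model has AUC 0.75, hs-cTnI adds 0.85 − 0.75 = 0.10.
- If it has AUC 0.85, hs-cTnI adds 0.85 − 0.85 = 0.

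The planned figure is the same in both cases.

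**3. Illustration for Section 20.** At the 10% NSTEMI prevalence assumed in Section 10, a model with no predictors gives every patient a probability of 0.10. All (100%) then fall below 0.3, and 100% − 10% = 90% of them are event-free. The rule-out figures therefore need a reference model before any part of them is credited to hs-cTnI.

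**4. Sample available for the missing comparison.** First, the plan's own figures (Section 10: sensitivity 95%, ±5%, prevalence 10%, 10% unusable data):
- Cases: 1.96² × 0.95 × 0.05 / 0.05² = 72.99, so 73 (matches).
- Analysed: 73 / 0.10 = 730 (matches).
- Included: 730 × 1.1 = 803, or 730 / 0.9 = 811.1, so 812. The stated 800 is a rounded figure close to both.

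Section 19 keeps one third for validation: 730 / 3 ≈ 243 patients and 73 / 3 ≈ 24 NSTEMI. The learning part has about 487 patients and 49 NSTEMI.

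**5. Precision of the AUC difference (with minus without hs-cTnI).** Simulation with 1,500 replicates. Assumptions: binormal scores, clinical score and troponin independent within outcome group, model scores taken as fixed, two-sided 5%, power by normal approximation.

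| Assumed AUC without → with | 243 patients, 24 events: CI half-width; power | 730 patients, 73 events: CI half-width; power |
|---|---|---|
| 0.70 → 0.75 | 0.073; 27% | 0.042; 65% |
| 0.75 → 0.80 | 0.066; 33% | 0.036; 78% |
| 0.75 → 0.85 | 0.086; 63% | 0.048; 98% |
| 0.80 → 0.90 | 0.074; 76% | 0.043; >99% |
| 0.75 → 0.90 | 0.095; 87% | 0.052; >99% |

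Only a large gain would be shown clearly in the validation third.

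**The case against.** The strongest defence is that the plan answers the question it sets. The process to be improved is the one in Figure 1, whose caption places it after emergency admission (the figure itself is not shown). Section 7 then spells out the aims: build the tool, compare it with HEART at 0h, and see whether it could replace the in-hospital evaluation at 0h. HEART is the proper comparator for replacement, and the NPV and PPV targets concern the tool as a whole. Nowhere does the SAP say that the HEART difference will be credited to hs-cTnI. On this view a model without hs-cTnI is an optional extra.

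Much of this stands. The quoted sentence is not an error, and the HEART comparison should stay. Two stronger readings that a reader might infer are not supported:
- That HEART is the tool's only comparator. Section 7 also plans the in-hospital troponin increment.
- That the study cannot address its hypothesis. Section 5 speaks only of interest for stratification, with no claim over a clinical-only model, and the primary objective addresses it through stand-alone discrimination.

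What the defence does not remove is the sentence in Section 7 on usefulness. It follows directly on the choice of capillary or venous method, so its natural subject is hs-cTnI. Replacing HEART with a tool that happens to contain hs-cTnI does not show what hs-cTnI contributed.

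Low precision is also a fair objection: a null result on 24 events could be misread as no benefit. That limits how the result is worded, and the HEART comparison, which is planned anyway, rests on the same sample.

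**Conclusion.** The point holds in a limited form. The SAP plans no model without pre-hospital hs-cTnI, so the test's added value over pre-hospital history and ECG cannot be estimated. That bears on one stated secondary aim, the usefulness of the chosen hs-cTnI method for improving rule-in and rule-out. The primary objective and the replacement question against HEART are untouched.

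The absence of the comparison is read directly from Sections 7 and 18 to 20 and rests on no assumption. The size of the ambiguity can only be illustrated (0.10 or nothing behind the same 0.05), because the SAP gives no AUCs. The precision figures depend on the assumed AUCs and on independence between troponin and the clinical score, and they leave out the uncertainty from fitting the models on about 49 learning events.

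**What to change.** - **Section 19:** in the learning sample, repeat the same LASSO procedure with the same candidates except hs-cTnI, and without its interaction with delay (delay itself stays). Fit both models on the same complete cases. On the same validation patients, report both AUCs and the difference, tool minus clinical-only, with a paired bootstrap 95% CI, in line with Section 13.
- **Section 20:** report the rule-out and rule-in shares, NPV and PPV for both models.
- **Interpretation:** present the difference as an estimate of added value beside the HEART comparison, not as the sole basis for judging usefulness. State in advance that a non-significant difference does not show that hs-cTnI adds nothing.
- **Optional:** add an optimism-corrected bootstrap or cross-validated estimate on the whole cohort, which would be more precise.

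Cost: SAP wording and one more model fit on data already collected, with no new patients or measurements. The downside is one more secondary comparison of low precision. It should be specified before the validation results are seen.
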